#### 7.1.2. LABORATORY DATA

Missing laboratory results will not be replaced.

---

Document:	\\\usadc-nas01a\cp_ops\PROJECTS\Glaxo SmithKline\GSK208109_BZA47109\SAP		
Author:	PPD	Version Number:	3.0

Template No: CS\_TP\_BS016 – Revision 5  
Effective Date: 01Apr2018

Reference: CS\_WI\_BS005

### 7.1.3. ADVERSE EVENTS

#### Solicited Adverse Events:

Daily recording of solicited adverse events: For symptom screens indicating the presence or absence of solicited adverse events, the following rules are applicable:

- Denominators for the summary of local (or general) solicited adverse events will be calculated using the number of subjects who respond “Yes” or “No” to the question concerning the occurrence of local (or general) adverse events.
- When a specific solicited adverse event is marked as having not occurred following a specific vaccination (i.e. SDTM CE.CEOCCUR=N for the specified post-vaccination period for the adverse event in question), all daily measurements will be imputed as Grade 0.
- When a specific solicited adverse event is marked as having occurred following a specific vaccination (i.e. SDTM CE.CEOCCUR=Y for the specified post-vaccination period for the adverse event in question), any missing daily recordings will be given imputed values to allow them to contribute to the ‘Any’ rows but not to specific grade rows of the solicited adverse event summary tables.
- When the occurrence of a specific solicited adverse event is not present (i.e. SDTM CE.CEOCCUR is neither Y nor N for the specified post-vaccination period for the symptom in question) but the group of solicited adverse events (local or general) is marked as having occurred (i.e. SDTM CE.CEOCCUR=Y), all missing daily recordings will be given imputed values to allow them to contribute to the ‘Any’ rows but not to specific grade rows of the solicited adverse event summary tables.

The following table shows how subjects contribute to each category for a specific solicited adverse event over the Day X to Day Y post-vaccination period:

Solicited adverse event category	Subjects included in the calculation of the numerator
Any	All subjects with at least one occurrence of the adverse event at grade 1, grade 2, or grade 3 between Day X and Day Y or with the adverse event marked as present and at least one missing daily recording between Day X and Day Y
At least grade 1	All subjects with at least one occurrence of the adverse event at grade 1, grade 2, or grade 3 between Day X and Day Y
At least grade 2	All subjects with at least one occurrence of the adverse event at grade 2 or grade 3 between Day X and Day Y
At least grade 3	All subjects with at least one occurrence of the adverse event at grade 3 between Day X and Day Y

### Unsolicited adverse events

Unsolicited adverse event summaries are including serious adverse events unless specified otherwise. Missing severity, relationship with study vaccine, and outcome of unsolicited adverse events will not be replaced and will appear as 'UNKNOWN' in all statistical listings.

## **7.2. DATA DERIVATION**

### **7.2.1. BODY MASS INDEX**

$$\text{BMI (kg/ m}^2\text{)} = \text{weight (kg)}/ \text{height (m)}^2$$

### **7.2.2. AGE AT VACCINATION IN YEARS**

When age at vaccination is to be displayed in years, it will be calculated as the number of complete calendar years between the date of birth and the date of vaccination. For example:

DOB = 10SEP1983, Date of vaccination = 09SEP2018 -> Age = 34 years

DOB = 10SEP1983, Date of vaccination = 10SEP2018 -> Age = 35 years

### **7.2.3. ONSET DAY**

The onset day for an event (e.g. AE, medication, vaccination) is the number of days between the last study vaccination and the start date of the event. This is 1 for an event occurring on the same day as a vaccination (and reported as starting after vaccination)

### **7.2.4. DURATION OF EVENTS**

The duration of an event with a start and end date will be the number of days between the start and end dates plus one day, i.e. an event that starts on 03MAR2018 and ends on 12MAR2018 has a duration of 10 days.

The duration of solicited events will be calculated as the sum of the individual days with the symptom reported at grade 1 or higher.

### **7.2.5. COUNTING RULES FOR COMBINING SOLICITED AND UNSOLICITED ADVERSE EVENTS**

For output combining solicited and unsolicited adverse events, all serious adverse events will be

Document:	\\\usadc-nas01a\cp_ops\PROJECTS\Glaxo SmithKline\GSK208109_BZA47109\SAP		
Author:	PPD	Version Number:	3.0

Template No: CS\_TP\_BS016 – Revision 5  
Effective Date: 01Apr2018

Reference: CS\_WI\_BS005

---

considered general events since the administration site flag is not included in the expedited adverse event CRF pages.

Multiple events with the same preferred term which start on the same day are counted as only one occurrence.

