4.6 Study Holding Criteria

4.6.1 Study Holding Rules

The safety holding rules which will be assessed by the Investigator are defined in [Table 11](#) and the safety holding rules which will be assessed by the iSRC are defined in [Table 12](#). The toxicity grading scales for hematology, biochemistry, and urinalysis parameters applicable for this study are presented in [Table 13](#).

Table 11 Holding Rules Assessed by the Investigator

Holding Rule	Event	Number of Subjects
1a	Death or any life-threatening SAE.	≥1
1b	Any withdrawal from the study following a Grade 3 AE that cannot reasonably be attributed to a cause other than vaccination.	≥1
1c	Any SAE or fever >40°C (104°F) that cannot reasonably be attributed to a cause other than vaccination, or visible necrosis at the injection site, within the 7-day (Day 1 to Day 7) period after vaccination.	≥1

AE = adverse event; SAE = serious adverse event.

Table 12 Holding Rules Assessed During Internal Safety Review Committee Evaluations

Holding Rule	Event	Percentage of Subjects
2a	Any Grade 3 solicited local AE (lasting 48 hours or more) in an investigational group, within the 7-day (Day 1 to Day 7) period after vaccination.	≥20% (per group)
2b	Any Grade 3 solicited general AE (lasting 48 hours or more) in an investigational group, that cannot reasonably be attributed to a cause other than vaccination, within the 7-day (Day 1 to Day 7) period after vaccination.	≥20% (per group)
2c	Any Grade 3 unsolicited AE in an investigational group, that cannot reasonably be attributed to a cause other than vaccination, within the 7-day (Day 1 to Day 7) period after vaccination.	≥20% (per group)
2d	Any Grade 3 abnormality in prespecified hematological or biochemical laboratory parameters in an investigational group within the 7-day (Day 1 to Day 7) period after vaccination (refer to Table 13).	≥20% (per group)

AE = adverse event.

[Figure 2](#) illustrates that, with 10 subjects per group:

- For holding rules 1a, 1b, and 1c, using a cutoff of 1/10, there is more than 80% chance that the holding rule is met for a vaccine with a true incidence rate above 15% and there is more than 60% chance that the holding rule is not met for a vaccine with a true incidence rate below 5%.
Since this holding rule will be assessed on a continuous basis by the Investigator, irrespective of the number of subjects enrolled, the statistical interpretation of this holding rule is less relevant.

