9.4.2 Safety Analyses

9.4.2.1 Primary Analyses

The primary analysis will be performed on the Exposed Set.

The percentage of subjects with at least 1 local AE (solicited and unsolicited), with at least 1 general AE (solicited and unsolicited) and with any AE during the 7-day or the 30-day follow-up period will be tabulated with exact 95% CI after each vaccination and overall. The percentage of doses followed by at least 1 local AE (solicited and unsolicited), by at least 1 general AE (solicited and unsolicited) and by any AE will be tabulated, overall vaccination course, with exact 95% CI. The same computations will be done for Grade 3, any AEs considered related to vaccination and any Grade 3 AEs considered related to vaccination.

The percentage of subjects/doses reporting each individual solicited local and general AE during the 7-day follow-up period will be tabulated with exact 95% CI as follows:

- Over the 2 or 3 doses, the percentage of subjects with the symptom and its exact 95% CI.
- Over the 2 or 3 doses, the percentage of doses with the symptom and its exact 95% CI.
- At each study dose (visit), the percentage of subjects with the symptom and its exact 95% CI.

Occurrence of fever will be reported per 0.5°C cumulative increments as from $\geq 38^{\circ}\text{C}$ as well as the occurrence of fever $>40^{\circ}\text{C}/104^{\circ}\text{F}$ with causal relationship to the study treatment.

The verbatim reports of unsolicited symptoms will be reviewed by a physician and the signs and symptoms will be coded according to the Medical Dictionary for Regulatory Activities (MedDRA). Every verbatim term will be matched with the appropriate preferred term. The percentage of subjects with unsolicited AEs within 30 days after any doses with its exact 95% CI will be tabulated by group and by MedDRA preferred term. Similar tabulation will be done for Grade 3 unsolicited AEs, for unsolicited AEs that resulted in a medically attended visit, for Grade 3 and causally related unsolicited AEs and for unsolicited AEs causally related to vaccination.

The number of subjects who experienced at least 1 SAE or any AE of specific interest (pIMD) during the entire study period will be reported.

For each group and for each hematology, biochemistry, and urinalysis parameter:

- The percentage of subjects having hematology, biochemistry, and urinalysis results below or above the local laboratory normal ranges will be tabulated by timepoint.

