
e) Is a congenital anomaly/birth defect in the offspring of a study subject
 
Medical or scientific judgment should be exercised in deciding whether reporting is appropriate in other situations, such as important medical events that may not be immediately life-threatening or result in death or hospitalization but may jeopardize the subject or may require medical or surgical intervention to prevent 1 of the other outcomes listed in the above definition. These should also be considered serious. Examples of such events are invasive or malignant cancers, intensive treatment in an emergency room or at home for allergic bronchospasm, blood dyscrasias or convulsions that do not result in hospitalization.

Solicited Adverse Events

a) Solicited local (injection site) AEs.
 
 • Pain at injection site. • Redness at injection site. • Swelling at injection site.

b) Solicited general AEs.
 
 • Fatigue. • Fever. • Gastrointestinal symptoms.* • Headache. • Myalgia. • Shivering. • Arthralgia.

*Gastrointestinal symptoms include nausea, vomiting, diarrhea, and/or abdominal pain.
 
Note: Subjects will be instructed to measure and record the oral body temperature in the evening. Should additional temperature measurements be performed at other times of day, subjects will be instructed to record the highest temperature in the diary card.

Unsolicited Adverse Events

An unsolicited AE is an AE that was not solicited using a Subject Diary and that was spontaneously communicated by subjects who has signed the informed consent.

Potential unsolicited AEs may be medically attended (defined as symptoms or illnesses requiring hospitalization, or emergency room visit, or visit to/by a health care provider) or were of concern to the subjects. In case of such events, subjects will be instructed to contact the study center as soon as possible to report the event(s). The detailed information about the reported unsolicited AEs will be collected by the qualified study center personnel during the interview and will be documented in the subject's records.

Unsolicited AEs that are not medically attended nor perceived as a concern by subjects will be collected during interview with the subjects and by review of available medical records at the next visit.

Adverse Events of Specific Interest

Potential immune-mediated Diseases

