#### **7.2.6. COUNTING RULES FOR OCCURRENCES OF SOLICITED ADVERSE EVENTS**

When the occurrences of solicited adverse events are summarized, each event recorded as having occurred during a specific period will be counted as only one occurrence regardless of the number of days on which it occurs.

For a given subject and the analysis of solicited symptoms within 7 days post-vaccination, missing or non-evaluable measurements will not be replaced. Therefore the analysis of the solicited will include only vaccinated subjects for doses with documented safety data (i.e., symptom screen completed). More specifically the following rules will be used:

- Subjects who documented the absence of a solicited symptom after one dose will be considered not having that symptom after that dose.
- Subjects who documented the presence of a solicited symptom and fully or partially recorded daily measurement over the solicited period will be included in the summaries at that dose and classified according to their maximum observed daily recording over the solicited period.
- Subjects who documented the presence of a solicited symptom after one dose without having recorded any daily measurement will be assigned to the lowest intensity category at that dose (i.e. 38°C for fever or grade 1 for other symptoms).
- Doses without symptom sheets documented will be excluded.

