### 16.1. ADVERSE EVENTS

Adverse Events (AEs) will be coded using Medical Dictionary for Regulatory Activities (MedDRA) central

---

Document:	\\usadc-nas01a\cp_ops\PROJECTS\Glaxo SmithKline\GSK208109_BZA47109\SAP		
Author:	PPD [REDACTED]	Version Number:	3.0
		Version Date:	27SEP2021

Template No: CS\_TP\_BS016 – Revision 5  
Effective Date: 01Apr2018

Reference: CS\_WI\_BS005

---

coding dictionary, Version 22.0.

The percentage of subjects with at least 1 local AE (solicited and unsolicited), with at least 1 general AE (solicited and unsolicited) and with any AE during the 7-day or the 30-day follow-up period will be tabulated with exact 95% CI after each vaccination and overall.

The percentage of doses followed by at least 1 local AE (solicited and unsolicited), by at least 1 general AE (solicited and unsolicited) and by any AE will be tabulated, overall vaccination course, with exact 95% CI. The same computations will be done for Grade 3, any AEs considered related to vaccination, any Grade 3 AEs considered related to vaccination and any AEs resulting in a medically attended visit.

The percentage of subjects/doses reporting each individual solicited local and general AE during the 7-day follow-up period will be tabulated with exact 95% CI as follows:

- Over the 2 or 3 doses, the percentage of subjects with the symptom and its exact 95% CI.
- Over the 2 or 3 doses, the percentage of doses with the symptom and its exact 95% CI.
- At each study dose (visit), the percentage of subjects with the symptom and its exact 95% CI.

Occurrence of fever will be reported per 0.5°C cumulative increments as from  $\geq 38^{\circ}\text{C}$  as well as the occurrence of fever  $>40^{\circ}\text{C}/104^{\circ}\text{F}$  with causal relationship to the study treatment.

The verbatim reports of unsolicited symptoms will be reviewed by a physician and the signs and symptoms will be coded per the Medical Dictionary for Regulatory Activities (MedDRA). Every verbatim term will be matched with the appropriate preferred term. The percentage of subjects with unsolicited AEs within 30 days after any doses with its exact 95% CI will be tabulated by group and by MedDRA preferred term. Similar tabulation will be done for Grade 3 unsolicited AEs, for unsolicited AEs that resulted in a medically attended visit, for Grade 3 and causally related unsolicited AEs and for unsolicited AEs causally related to vaccination. These tabulations will include SOC and SOC/PT analyses.

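### In the combined local/general AE tables, SAP 7.2.5 counts a serious injection-site event as general only because the expedited CRF page has no site flag

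*SAP*

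**What the plan says.** The rule is one sentence in SAP 7.2.5. It opens with its scope, "For output combining solicited and unsolicited adverse events, all serious adverse events will be", and continues with the classification and the reason: "considered general events since the administration site flag is not included in the expedited adverse event CRF pages". The next sentence of that section counts events that share a preferred term and a start day only once.

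The main output of this kind is described in SAP 16.1: "The percentage of subjects with at least 1 local AE (solicited and unsolicited), with at least 1 general AE (solicited and unsolicited"), together with any AE, over the 7-day or 30-day follow-up period, after each vaccination and overall. Per-dose percentages follow, and then: "The same computations will be done for Grade 3, any AEs considered related to vaccination", with Grade 3 related and medically attended versions as well.

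Protocol 9.4.2.1 plans the same local and general rows as part of the primary safety analysis but contains no rule that serious events count as general. SAP 3.3, which lists changes from the protocol, does not mention it.

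**The concern.** Whether an event is local or general is a fact about where it occurred. SAP 7.2.5 settles it by which CRF page the event was reported on. A serious event at the injection site is then labelled systemic in the tables that a reader uses to compare local with general tolerability.

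The protocol foresees an event of this type. Holding rule 1c in Table 11 names "or visible necrosis at the injection site, within the 7-day (Day 1 to Day 7) period after vaccination". Necrosis is not among the solicited local events in Appendix 6, which are pain ("Pain at injection site"), redness and swelling, so it need not have a diary entry of its own. If it met a seriousness criterion, the combined tables would show it as general. The local/general split also matters here because Protocol 4.3 expects reactogenicity to increase after a second or third dose of the same adjuvanted vaccine.

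**Working it through.** **Step 1. Which outputs the rule reaches.**

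| Output | Where planned | Reached? |
|---|---|---|
| At least one local AE; at least one general AE (by subject and by dose; all, Grade 3, related, Grade 3 related, medically attended) | Protocol 9.4.2.1, SAP 16.1 | Yes |
| Any-AE row of the same tables | same | No: the event counts under either label |
| Individual solicited local AEs | same | No: not combined output |
| Unsolicited AEs by SOC/PT, which include serious events | SAP 7.1.3, 16.1 | No: not split local/general |
| SAE counts and listing | SAP 16.1, 16.1.2 | No |
| Holding rules | Protocol Tables 11 and 12 | No: none uses the combined rows |

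On the third row of the table, the protocol says: "The percentage of subjects/doses reporting each individual solicited local and general AE during the 7-day follow-up period will be tabulated". Under SAP 7.2.6 these data come from the symptom screens, and subjects with daily recordings are "classified according to their maximum observed daily recording over the solicited period".

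**Step 2. Which events it moves.** Appendix 6 defines serious by outcome, and intensity is graded separately. The rule therefore acts on seriousness: a Grade 3 local reaction that is not serious stays local.

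**Step 3. When a row changes.** The rows count subjects with at least one event. A subject drops out of a local row only if no other local event in the window qualifies for that row, and is added to the general row only if no other general event qualifies. Appendix 6 treats all solicited local reactions as related to vaccination. One diary entry of mild pain therefore keeps the subject in both the all-grades and the related local rows. The Grade 3 rows are the most exposed.

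**Step 4. The plan's own figures.** Protocol 9.2 gives 45 subjects per active arm aged 50-70 and exact Clopper-Pearson 95% limits.

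- P(at least one event) = 1 - (1 - p)^45. At p = 3.5% this is 79.9%; at p = 5.0% it is 90.1%. The protocol states 80% and 90%.
- For x = 0 the upper limit is 1 - 0.025^(1/45) = 7.9%. For x = 1 the limits are the 2.5% quantile of Beta(1, 45) = 0.1% and the 97.5% quantile of Beta(2, 44) = 11.8%. Both rows match Table 22.

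**Step 5. Size per affected subject.** The shift is 1/n. The case shown is one serious injection-site event in a subject with no other qualifying local event, in an otherwise empty row.

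| n | Row under SAP 7.2.5 | Row if classed by site | Shift |
|---|---|---|---|
| 45 (active arm, 50-70 years) | 0.0% (0.0-7.9) | 2.2% (0.1-11.8) | 2.2 points |
| 35 (planned Step 4 adjuvanted group) | 0.0% (0.0-10.0) | 2.9% (0.1-14.9) | 2.9 points |
| 25 (planned Step 4 unadjuvanted group) | 0.0% (0.0-13.7) | 4.0% (0.1-20.4) | 4.0 points |
| 10 (antigen group, 18-45 years) | 0.0% (0.0-30.8) | 10.0% (0.3-44.5) | 10.0 points |

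The rows for 35 and 25 are the largest denominators available for Dose 3.

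**Step 6. How often it could arise.** The documents give no rate of serious injection-site events. Taking 0.1% to 2% per subject as an assumption, the chance of at least one among the 90 active subjects aged 50-70 is 1 - (1 - p)^90: 8.6% at 0.1%, 36.3% at 0.5%, 59.5% at 1% and 83.8% at 2%. The range is deliberately wide and is not an estimate. The chance that a row changes is lower still, because of the conditions in Step 3.

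**Step 7. Double recording.** If one reaction is on both the diary and the expedited page, SAP 7.2.5 merges same-day records with the same preferred term but does not say whether the merged record is local or general.

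**The case against.** The rule is prespecified, mechanical and openly explained. The combined rows are not among the endpoints in Protocol Table 9, which lists solicited local symptoms, solicited general symptoms, unsolicited events, SAEs, events of specific interest and laboratory parameters separately. No serious event disappears: each stays in the any-AE row (within its window) and in the SAE listing. The alternative needs judgement. The documents do not say that the preferred term identifies the site, and Appendix 6 asks the investigator to record a diagnosis in preference to individual signs and symptoms, so the term may not name the injection site. On this view a footnote would be enough.

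Most of this stands, and it sets the size of the point. It does not make the label right: a prespecified rule can still put an event in the wrong row. The judgement needed is small, because Protocol 9.4.2.1 and SAP 16.1 already have a physician review the unsolicited verbatim terms.

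Two stronger readings are tempting, and the documents do not support them. A reader might infer that the most severe injection-site reactions leave the local tables. They do not: the rule selects on seriousness, covers combined outputs only, and leaves the individual solicited local tables alone. A reader might also infer from rule 1c that a safety signal could be masked. It would not be: rules 1a to 1c are triggered by single events that the investigator assesses. Rule 1c also names necrosis separately from SAEs, so necrosis is not automatically serious and not automatically moved.

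**Conclusion.** The point holds as a minor misclassification. A serious injection-site event would be placed in the wrong row of the combined local and general tables because a CRF field is missing. In an arm of 45 the cost is at most 2.2 points per affected subject in the local row. The general row rises by the same amount only if that subject has no other qualifying general event. No listed primary endpoint, SAE report or holding decision changes.

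The conclusion rests on the wording of SAP 7.2.5 and on planned group sizes. That such events will be few is an assumption, since the documents give no rate.

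**What to change.** Replace the sentence in SAP 7.2.5 with:

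> In combined outputs, a serious AE is classed as local when its MedDRA preferred term or medically reviewed verbatim places it at the injection site, and as general otherwise; the classification is made before database lock by a reviewer without access to treatment codes. A reaction recorded on both the diary and the expedited page is counted once, as local.

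If the present rule is kept, footnote the combined tables with the number of serious injection-site events counted as general, and list the rule in SAP 3.3.

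The cost is a short SAP edit and a check of what should be a few SAEs, with no new data collection. SAP 4.4 already has all previous analyses re-produced at the final analysis, so the correction can be carried through the interim tables then. The downside is that a brief case-by-case review replaces a mechanical rule.
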